Although the core FDAC model is the same, there are some differences in the implementation of the intervention across sites. For example, some sites have started providing support in pre-proceedings (London and Kent) or post-proceedings (Gloucestershire). Some sites also use peer-mentoring, where successful parents support parents in care-proceedings. This study focuses on the overall effectiveness of FDAC across sites.

Separate evaluations are being conducted on behalf of the What Works Centre for Social Care which will explore these variations in greater detail:

- Peer-mentoring; evaluated by King's College London.
- Post-proceedings support in the Gloucestershire FDAC; evaluated by the University of Sussex.
- Engagement with FDAC using behavioural insights; evaluated by the Centre for Evidence Implementation.

Impact Evaluation

Research questions

The impact evaluation will seek to answer the following questions:

RQ1 What is the impact of FDAC on the likelihood that children are reunited with their parents at the end of care proceedings relative to non-FDAC care proceedings as usual?

RQ2 What is the impact of FDAC on the likelihood that parents continue to misuse alcohol or drugs by the end of care proceedings relative to non-FDAC care proceedings as usual?

RQ3 What proportion of children reunified at the end of FDAC care proceedings are still placed with their parent(s) three years after final court hearing and how does this compare with the national average?

RQ4 What is the impact of FDAC on the likelihood of final care proceedings hearings being contested relative to non-FDAC care proceedings as usual?

RQ5 What is the impact of FDAC on the likelihood of external expert witnesses being consulted during care-proceedings relative to non-FDAC care proceedings as usual?

RQ6 What is the impact of FDAC on the placement of the child at the end of care proceedings relative to non-FDAC care proceedings as usual?

Participants

Study participants will be drawn from 14 FDAC sites (for the intervention group) and from 12 Local Authorities (for the control group). Participants in the intervention group will be those

going through FDAC court proceedings. Control cases will be selected from non-FDAC care proceedings as usual cases.

Eligibility for study inclusion² is defined as the following:

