- **Intervention** – all cases that have been referred to an FDAC that were open between October 2019³ and June 2022 and a final hearing took place by October 2022 will be considered eligible.
- **Control** – any case that meets the basic criteria for an FDAC referral and sits within an area covered by a Local Authority⁴ that has an FDAC but receives non-FDAC care proceedings as usual that were open between October 2019 and June 2022 and a final hearing took place by October 2022 will be considered eligible.

The basic criterion for FDAC referral is that “Parental substance misuse (drugs or alcohol or both) is a key factor of the Local Authority’s concerns about the child(ren) within a care proceedings case”. This will be captured for FDAC cases from a suite of variables, including:

- Current or historical misuse of drugs or alcohol
- Substance misuse type
- Severity of alcohol misuse
- Severity of drug misuse

This data is not systematically collected by Local Authorities for non-FDAC cases. Instead, care proceedings case data is typically recorded in court bundles and case notes. In June 2022, we distributed a survey to Local Authorities to determine which data fields for non-FDAC cases exist in their records, whether Local Authorities have direct access to that information, and whether it would be feasible for them to provide data for those fields. Based on their responses, we adjusted the data collection template and revised the study protocol. Some FDAC sites have developed their own referral inclusion and exclusion criteria though the variation between sites has never been closely documented. For instance, some FDAC sites exclude cases where parental psychosis or litigation capacity may act as a barrier to parental engagement with FDAC or where there is a history of severe physical or sexual abuse of a child. Furthermore, the selection process likely varies by FDAC site in regard to subjective components that are not included within the criteria. There is therefore likely to be a degree of selection bias, with systematic differences between control and treatment participants.

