The unit of analysis varies across outcomes. The primary outcome (reunification) is defined at the child-level while secondary outcomes are defined at either the parent-level (i.e. parental substance cessation) or case-level (i.e. contested hearing and the use of expert witnesses). Matching will be implemented separately for outcomes at different units of analysis. Child-level outcomes will include covariates about the child (such as age) and parent characteristics (mainly about primary carer's characteristics such as alcohol and drug misuse at baseline). Parent-level outcomes will include case characteristics (i.e. date of issue) and parent-level covariates (e.g. age, gender, substance misuse, and for how many children they are primary carer).⁶ Case-level outcomes will include case characteristics, including date of issue, aggregated parent-level (e.g. primary carer age, gender, ethnicity) and aggregated child-level characteristics (e.g. how many children in the case).

Comparisons will be made using the original uncoarsened covariates, with differences reported as *Hedges' g* effect sizes. If we observe an imbalance with an effect size of greater than 0.05, we will revise the matching specification by adjusting the coarsening of any variables with an imbalance of greater than 0.05. We will reduce the number of coarsening categories (unless the variable in question is already uncoarsened). If this does not resolve the imbalance, we will coarsen the variable further instead.

We will also use the multivariate L1 distance statistic before and after matching to describe the quality of the matching. This statistic measures the overall imbalance with respect to the joint distribution, including all interactions, of the covariates (Blackwell et al., 2010). The smaller L1, the less the imbalance across the covariates, with L1=0 indicating perfect balance and L1=1 complete separation across covariates.

Data sources and availability

The data to be used for matching and the evaluation of outcomes will be collected from several sources:

- The FDAC data collection tool, for FDAC cases
- Local Authority case management systems, typically within children's social care and legal teams
- Case notes, typically held by Local Authorities and courts

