Data collected as part of the FDAC data collection tool will be the source of data for intervention cases. Ideally, data for the control group would be collected from the same data source, however Local Authorities do not systematically collect all the information collected by FDAC sites. Local Authorities will be asked to provide comparable data from their own case management systems and case notes based on a template developed by NatGen. As far as is possible, we will aim for comparable data collection. For example, we will collect data from fields used in statutory returns, such as those collected in the Children in Need census. Fields collected by control sites will be more limited relative to intervention sites. For

⁵ Although the CONSORT *Statement* was originally developed to guide the reporting of RCTs, many of its components also apply to other types of quasi-experimental impact studies. A flow diagram template will be downloaded from <http://www.consort-statement.org/>.

⁶

example, drug misuse will be based on data collected by Local Authorities, which may not be as accurate as the testing conducted in FDAC sites (e.g. drug testing using samples of parent's hair).

Our data collection template that will be completed by the Local Authorities will include detailed instructions and guidance for all key fields required to complete this evaluation. There will be cell validation in order to minimise blank cells and ensure data comparability across Local Authorities. We will only be able to use fields collected in both FDAC sites and Local Authorities in the matching.

Key characteristics that we intend to include in the matching are illustrated in Table 3. Each of these characteristics are collected in both the FDAC data collection tool and the control group data collection tool. These variables are important indicators of whether a case is suitable for FDAC (such as type of drug and alcohol misuse). However, it cannot account for subjective criteria that may be used by FDAC sites in determining which cases should be supported by FDAC. Table 3 also outlines how specific variables will be coarsened in matching.

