- That 25% of children in control are reunified with their parents by the end of care-proceedings (informed by Harwin et al., 2018)
- A type one error rate of 0.05
- Power of 0.80 (a type two error rate of 0.20)
- Two tailed significance testing

There is some uncertainty on the expected sample size. Based on Harwin et al. (2018) we anticipate that each FDAC case will have a mean of 1.4 children. Our assumptions use this figure and build on estimates of expected caseloads for the implementation period (January 2021 – June 2022) collected by FDAC sites by CJI in Summer 2020. Based on updated figures concerning expected caseloads, we anticipate a sample of 300 intervention children from 215 cases.

Based on these assumptions, we expect the evaluation will be powered to detect a relative risk ratio of 1.36 (or equivalent to a 9.1 percentage point difference). No power calculations are conducted for secondary analyses, but these will have lower power as the units of analyses are at the parent and case-levels. However, as the intracluster correlation coefficient is relatively large for child-level analyses, the reduction in power will be relatively small.

Table 5 Minimum detectable effect size calculation		
Relative Risk Ratio		1.36
Baseline/Endline correlations	Child	0.45
	Parent	0.32
Intracluster correlations (ICCs)	Parent	0.70
		0.00

⁷ Our sample size calculations include estimates of the proportion of variance explained through the included covariates at each of these levels (R^2). We have converted these into pre- post-test correlations by taking the square root of the R^2 value.

Social Worker Team		0.00
Alpha		0.05
Power		0.80
One-sided or two-sided?		2
Level of intervention clustering		Parent
Average cluster size (parent)		1.40
Sample Size (children)*	Intervention	300
	Control	300
	Total	600
Sample Size (cases)	Intervention	215
	Control	215
	Total	430

* Of which, we assume half are intervention children and half are matched control children

Outcome measures

The primary and secondary outcomes will be sourced from the FDAC data collection tool for intervention cases and Local Authority administrative data for control cases. Local Authorities will already collect data on reunification but may not systematically capture parental alcohol or substance misuse, contested final hearing and use of expert witnesses. This will be included in the data collection template prepared by NatGen.

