Each of these outcomes will be analysed as binary variables with the unit of analysis at parent (or case) level. The sample for the analysis on cessation will include only parents who had substance misuse issues at baseline. If the use of expert witnesses is recorded as a count variable (i.e. the number of witnesses used) we will dichotomise the variable for this analysis. These outcomes will therefore be analysed using a multilevel logistic regression model, using an approach consistent with the binary analysis:

⁹ By definition, it is not possible to assess if there are associations with unobserved characteristics. If there were associations with unobserved characteristics, the data would be described as missing not at random (MNAR). In this case, both the primary analysis and multiple imputation would produce biased estimates. A full description of types of missing data and their consequences are available in the WWCS statistical analysis guidance.

$$(1) P(Cessation_{pcs}) = \text{logit}^{-1}(\beta_0 + \beta_1 \text{Intervention}_{pcs} + \beta_2 X_{pcs} + u_{cs} + u_s)$$

$$(2) P(Contested_{cs}) = \text{logit}^{-1}(\beta_0 + \beta_1 \text{Intervention}_{cs} + \beta_2 X_{cs} + u_s)$$

$$(3) P(Experts_{cs}) = \text{logit}^{-1}(\beta_0 + \beta_1 \text{Intervention}_{cs} + \beta_2 X_{cs} + u_s)$$

The total number of different types of expert witness will otherwise be analysed using a multilevel Poisson regression, with overdispersion adjustment where appropriate. The model notation is as follows:

$$(4) \text{ExpertTypes}_{cs} = \exp(\beta_0 + \beta_1 \text{Intervention}_{cs} + \beta_2 X_{cs} + u_s)$$

Where u_s represents the random effects and are assumed to be normally distributed with 0 mean. The risk ratio will be estimated using the *meglm* command in Stata.

Effect Size Estimation

For binary outcomes in this study, we will report the relative risk ratios (RRR), using the following formula:

$$RRR = \frac{P(\text{Reunified} | \text{FDAC}, X)}{P(\text{Reunified} | \text{non-FDAC}, X)}$$

Where the numerator is the probability of reunification for FDAC cases conditional on covariates (denoted X in the formula), and the denominator is the probability of reunification for non-FDAC cases conditional on the same set of covariates.

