
Judicial and court time
 
 Judges time Court staff and administration times Listing office time 	
Operational activity
 
 FDAC Team attendance at court Pre-court meetings Day assessment with each family in 1st week of proceedings. Team organise IPMs and and chair review IPMS, and file minutes Team write initial parenting report, review reports and review parenting assessment report, minutes of meetings and circulate to all parties and court. The FDAC team hold regular key work, using MI and other interventions. The FDAC team chair Children's Needs meeting within first 10 weeks, and file minutes. Recruit, train and supervise parent mentors Organise and ensure team attendance at reflective supervision Drug treatment and testing Child psychiatry 	
 All parents met at court for first hearing by FDAC team All parents meet their allocated FDAC Judge and continue to meet same Judge throughout proceedings All parents have initial assessment by multi-disciplinary team within first 4 weeks FDAC team will formulate each case as a multidisciplinary team. All parents have an Intervention planning meeting within 4 weeks, and attended by FDAC team, parents, children's services, Guardian and treatment providers where possible. Initial Parenting assessment report and intervention plan presented to Court for 2nd Hearing. Once parents signed up to FDAC, parents proceed with regular fortnightly Non-Lawyer reviews Continuous monitoring and support by a therapeutic team, including regular testing, keywork and review reports. All parents will have a review IPM held at 10 weeks and 18 weeks. All parents will have been offered interventions delivered by local services and the FDAC team matched to their needs. All parents have a review parenting assessment report filed with Court for the IRH, which will include final recommendations, and options for post proceedings support. All parents will have had a time-limited highly coordinated therapeutic 'trial for change' by the end of proceedings Parent mentors will be present at Court and all parents will be offered option of support from a parent mentor. Team attend reflective supervision every 8 weeks Team and Judges will have attended initial and follow up training on a regular basis Team and Judges will be mindful of timescales and the National requirements Problem solving court approach is embedded in local court Parties recognise expertise of FDAC team 	
Parents' outcomes in FDAC as opposed to normal proceedings
 
 More engagement of parents in the court processes and with treatment and other services More parents are able to cease misusing substances and sustain their recovery More parents are able to resume care of their children More parents show improvement in their mental health More parents and children are protected from the impact of domestic abuse More improved relationships between parents and children even when children are not going to return home More parents have insight into why they have not been reunited with their children 		
Proportion of parents who have ceased substance misuse at end of proceedings

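### RQ2 takes parental misuse at the end of proceedings from a different source in each arm, and no planned analysis deals with the unequal detection this may bring

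*Supplement*

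**What the plan says.** All references are to protocol version 2.0.

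- Research questions: RQ2 is causal. It asks "What is the impact of FDAC on the likelihood that parents continue to misuse alcohol or drugs by the end of care proceedings", relative to usual proceedings.
- Outcome measures: the source is set by arm, in that "secondary outcomes will be sourced from the FDAC data collection tool for intervention cases and Local Authority administrative data for control cases". The same paragraph says that Local Authorities "may not systematically capture parental alcohol or substance misuse, contested final hearing and use of expert witnesses", and that the evaluator's template will ask for these items.
- Data sources and availability: the section covers outcomes as well as matching variables ("The data to be used for matching and the evaluation of outcomes will be collected from several sources"). It says that in the control group "drug misuse will be based on data collected by Local Authorities, which may not be as accurate as the testing conducted in FDAC sites", with hair samples as the example of FDAC testing. It also describes a template with guidance for the key fields and cell validation.
- Participants: for non-FDAC cases, "care proceedings case data is typically recorded in court bundles and case notes".
- Appendix A lists among FDAC outputs: "Continuous monitoring and support by a therapeutic team, including regular testing, keywork and review reports".
- Outcome measures defines the RQ2 outcome as binary, with 1 for a parent still misusing. It gives no common method of ascertainment, no look-back window and no rule for a parent without a recent assessment.
- Secondary Analysis fits the same kind of weighted multilevel logistic model as for the other binary outcomes. It adds: "The sample for the analysis on cessation will include only parents who had substance misuse issues at baseline".

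**The concern.** The source of the outcome coincides exactly with treatment. If misuse is detected more completely in one arm, the recorded rates differ even when the true rates do not. Coarsened exact matching and covariate adjustment balance baseline characteristics. They do nothing about an outcome recorded with different error in each arm.

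The direction cannot be settled in advance. Misuse missed in control records makes FDAC look worse. A note of misuse carried forward in control records without reassessment makes FDAC look better.

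The planned sensitivity analyses cover further coarsening, dropping covariates from the reunification model, and missing primary outcome data. None concerns how the RQ2 outcome is measured. The plan discloses the limitation of the data but does not carry it through to RQ2, whose result would be reported as an impact of FDAC.

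**Working it through.** **The plan's own figure.** There is none for RQ2: the plan makes no power calculation for secondary outcomes. Its only design figure is a detectable ratio of 1.36 for reunification. It reproduces with R-squared 0.10 on the between-parent term and 0.20 on the within-parent term, and with an exponential conversion to the odds ratio:

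- MDES = 2.80 × √(0.70×0.90/(0.25×430) + 0.30×0.80/(0.25×430×1.4)) = 0.242
- OR = exp(0.242×π/√3) = 1.55
- RRR = 1.55/(0.75 + 0.25×1.55) = 1.36, or 9.1 points on 25%

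It concerns another outcome and plays no part below.

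**Inputs.** The documents give no sensitivity, specificity, testing frequency or misuse rate for either arm. All values below are assumptions for illustration.

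**Formulae.** Let p be the true misuse rate, Se the sensitivity and Sp the specificity in an arm.

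- Recorded misuse = p×Se + (1−p)×(1−Sp)
- Misuse ratio = recorded misuse in FDAC / recorded misuse in controls
- Cessation ratio = (1 − recorded misuse in FDAC) / (1 − recorded misuse in controls)

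Both ratios are shown because Table 2 codes the outcome as misuse ceased, while Outcome measures codes 1 as still misusing.

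**Case 1: no true effect, misuse missed in controls.** p = 0.60 in both arms, Sp = 1 in both, FDAC Se = 0.95. Recorded FDAC misuse is 0.60×0.95 = 0.57.

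| Control Se | Recorded control misuse | Misuse ratio | Cessation ratio | Chance of p<0.05 |
|---|---|---|---|---|
| 0.90 | 0.54 | 0.57/0.54 = 1.06 | 0.43/0.46 = 0.94 | about 9% |
| 0.80 | 0.48 | 0.57/0.48 = 1.19 | 0.43/0.52 = 0.83 | about 46% |
| 0.70 | 0.42 | 0.57/0.42 = 1.36 | 0.43/0.58 = 0.74 | about 88% |

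The true ratio is 1.00 throughout. The last column is for a two-sided 5% test with 215 parents per arm. It borrows the plan's number of cases and ignores clustering and weighting. With Sp = 1 the misuse ratio is simply 0.95 divided by control Se, whatever the value of p. The cessation ratio does depend on p: at p = 0.40 it is 0.97, 0.91 and 0.86.

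**Case 2: no true effect, outdated misuse notes in controls.** p = 0.60 and Se = 0.95 in both arms, Sp = 0.95 in FDAC and 0.80 in controls.

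- FDAC: 0.57 + 0.40×0.05 = 0.59
- Control: 0.57 + 0.40×0.20 = 0.65
- Misuse ratio 0.59/0.65 = 0.91; cessation ratio 0.41/0.35 = 1.17

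**Case 3: a true benefit.** Misuse 50% in FDAC and 60% in controls, so the true cessation ratio is 0.50/0.40 = 1.25. Sp = 1 in both arms.

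- Se 0.95 in both: 0.525/0.43 = 1.22
- Se 0.95 against 0.80: 0.525/0.52 = 1.01
- Se 0.95 against 0.70: 0.525/0.58 = 0.91

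Equal imperfection costs little. Unequal detection can hide or reverse the benefit.

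**The case against.** The strongest reply is that the documents do not describe a tested arm set against an untested one. A reader might infer that the FDAC outcome is defined by a test result. It is not: Outcome measures describes binary indicators that used to feed a clinical judgement, and the severity guidance in Appendix D grades patterns of use without naming a test. Regular testing is an activity of the intervention and may inform the record. A reader might also infer that control parents go untested. The documents do not say so, and court bundles may hold test results. The statement on accuracy is hedged and names drugs only; the one on systematic capture is hedged too, though it covers alcohol. All of this stands.

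The plan also has mitigation: template guidance, cell validation, recoding of baseline severity into type of misuse, and a simple binary outcome. It commits the final report to lessons learned on data availability. These steps reduce differences in coding. They cannot supply a detection that was never made, or update a note that was never revised.

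Finally, every error rate above is assumed, and at a control sensitivity of 0.90 the distortion is small. That stands as well, and it is why a range is needed rather than a single correction.

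**Conclusion.** The concern holds in a limited form. Sources differ by arm, the plan itself says that control drug data may be less accurate, testing is part of the intervention, and no planned analysis addresses outcome error that differs by arm. The RQ2 ratio may therefore partly reflect detection.

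Under the stated assumptions and no true effect, the misuse ratio ranges from 1.06 to 1.36 when control records miss misuse. The cessation ratio is 1.17 when control notes are out of date. The documents fix neither the size nor the direction.

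Two stronger readings are not supported. One is that no RQ2 result could be interpreted at all; that depends on unknown error rates and on the size of the observed effect. The other is that the distortion matches the detectable effect of the study. The 1.36 in the plan belongs to reunification at a 25% control rate, its match with 0.95/0.70 is a coincidence, and the milder scenarios fall short of it.

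This is a secondary outcome, but a named research question, and its result could be misread either way.

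**What to change.** Add to Secondary Analysis a pre-specified quantitative bias analysis for RQ2.

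1. State ranges for each arm, for example control sensitivity 0.6 to 1.0 and specificity 0.8 to 1.0, with FDAC at 0.9 to 1.0 for both.
2. For each combination, correct the rate in each arm by (recorded rate + Sp − 1)/(Se + Sp − 1) and recompute the RRR. The two fitted probabilities that Effect Size Estimation already produces can serve as the recorded rates.
3. Exclude combinations incompatible with the data. For example, a recorded control rate of 65% with Se 0.6 and Sp 1 would imply a true rate of 0.65/0.60, above 100%.
4. Report the range of the RRR and where it crosses 1, and state whether the ratio is for misuse or for cessation.
5. Describe the RQ2 estimate as the effect on recorded misuse.

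Restricting RQ2 to parents whose status rests on the same kind of evidence in both arms is not advised as the remedy. The kind of evidence arises after baseline and is itself influenced by arm, so selection could replace misclassification. It would also need a further field from Local Authorities, whose template was already cut back.

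The cost is a little more analysis on data already planned, and a more cautious RQ2 conclusion. One limit remains: entry to the RQ2 sample depends on baseline misuse recorded from the same unequal sources, and a bias analysis of the outcome does not mend that. The report should say so.
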